Once the investigator determines that a stable dose and regimen has been achieved, XYWAV may be taken with or without food. If needed, XYWAV may be titrated to an optimized dose and regimen based on efficacy and tolerability, under the advisement and instruction from the investigator, with the goal to end the period with ≥ 2 weeks of optimized therapy on XYWAV.

Safety Follow-up Period

Following the Intervention period, participants will return for a Safety Follow-up visit 2 weeks after the End of Treatment (ET) or Early Discontinuation (E/D). Following the ET or E/D, including during the Safety Follow-up period, it is understood and expected that investigators will determine the appropriate course of care with the participant, and may resume any prescribed medications that were discontinued prior or during the study. There is no plan to monitor participants beyond the 2-week Safety Follow-up period.

Figure 1 Overall Design of Study JZP258-401

^{*}Adjustment to achieve optimal clinical benefit, with adequate control of cataplexy and EDS while maintaining tolerability per investigator judgment.

Abbreviation: EDS = excessive daytime sleepiness; wks = weeks

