9.1.4. Dose and Regimen Changes in Intervention Period

Time to optimize dose and regimen is defined as the time (unit is day) from the first dose and regimen of XYWAV to the optimized dose and regimen of XYWAV, where the optimized dose and regimen is the final dose and regimen that remains unchanged throughout the remainder of the intervention period. Optimized dose and regimen is defined as follows:

- The final dose and regimen that a participant takes before or at Visit 7 that remains unchanged to Visit 8 when the participant completes the XYWAV treatment, regardless of the time between Visits 7 and 8.
- The final dose and regimen that remains the same for at least 2 weeks (14 days) for a participant who completes at least 21 days post conversion and then terminates the XYWAV treatment early. For example, a participant changes dose and/or regimen after 1 week (7 days) post conversion and terminates from the study at Day 38, but remains on stable dose and regimen from Day 24 to Day 37.

Summary of dose and regimen changes will be based on XYWAV Safety analysis set per below:

The time to achieve optimized dose and regimen will be summarized with number of participants, mean, SD, median, minimum, maximum.

The number of changes in dose and regimen from first XYWAV dose to achieve optimized dose and regimen will be summarized with mean, SD, median, minimum, maximum.

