9.1.7. Subgroup Analyses

Unless specified, all endpoints will be summarized separately for participants identified as NT1 and NT2. Cataplexy attacks, ESS and PGIc will be summarized separately for those who achieved optimized dose and those that did not achieve optimized dose. Summary tables of statistics will be produced as described in Sections 9.1.1 through 9.1.3.

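### SAP 9.1.4 ignores why XYWAV was stopped, so a participant who quits for an adverse event or lack of effect after at least 21 days, with the final dose stable for at least 14, counts as optimized

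*SAP*

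**What the plan says.** SAP 9.1.4 starts from the general definition that "the optimized dose and regimen is the final dose and regimen that remains unchanged throughout the remainder of the intervention period". Two bullets then make it operational. The first covers completers: the dose and regimen in place by Visit 7 and still in place at Visit 8. The second applies "for a participant who completes at least 21 days post conversion and then terminates the XYWAV treatment early", and asks only that the final dose and regimen was the same for at least 14 days. Neither bullet mentions the reason for stopping. The worked example is a participant who changes dose after a week, then "terminates from the study at Day 38, but remains on stable dose and regimen from Day 24 to Day 37".

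On the population: "Summary of dose and regimen changes will be based on XYWAV Safety analysis set per below". On the statistics: "The time to achieve optimized dose and regimen will be summarized with number of participants, mean, SD, median, minimum, maximum". There is no failure or censoring rule, and SAP 9.1.6 plans no sensitivity analysis.

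The optimized status is used again in SAP 9.1.7, where cataplexy, ESS and PGIc "will be summarized separately for those who achieved optimized dose and those that did not achieve optimized dose".

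On what optimization means, SAP 5.2 and Protocol 4.1 describe titration guided by efficacy and tolerability. The footnote to the design figure in both documents reads "Adjustment to achieve optimal clinical benefit, with adequate control of cataplexy and EDS while maintaining tolerability per investigator judgment".

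**The concern.** A participant who gives up XYWAV because it does not work or is not tolerated has not reached a dose that is optimized in the sense of SAP 5.2. Protocol 2.3.1 names worse disease control and reduced tolerability as risks of the switch, so such participants are foreseen. The second bullet nevertheless classes them as optimized once the two duration conditions are met.

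Time to optimized dose and number of changes are key endpoints for the treatment-optimization objective. The Protocol Introduction treats switching with few or no dose changes as success. A failure on a never-changed dose therefore looks like the ideal switch. The same person's outcomes then sit on the wrong side of the achieved/not achieved split. The study is descriptive, may support label discussions (Protocol 4.1) and may be presented externally at an interim look (SAP 5.5), so these summaries are the product itself.

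**Working it through.** **1. The rule and the SAP's own example.** Let D be days on XYWAV at the stop and c the day after conversion of the last change (c = 0 if there was none). The second bullet gives optimized status if D ≥ 21 and D − c ≥ 14, with time to optimized dose = c. First XYWAV dose: night of Day 15 (SAP 7.2.2).

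- Day 24 to Day 37 is 37 − 24 + 1 = 14 days, so the stability condition is met.
- Day 38 − Day 15 = 23 ≥ 21, so the duration condition is met.
- Time to optimized dose = 24 − 15 = 9 days (22 − 15 = 7 if the change is dated to Day 22), with 1 change.

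The example agrees with its rule.

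**2. Who qualifies.**

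| Stop after D days | Qualifies if last change on or before day (D − 14) |
|---|---|
| 14 or 20 | never (D < 21) |
| 21 | 7 |
| 28 | 14 |
| 35 | 21 |

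A participant who never changes dose and stops for an adverse event on Day 37 has D = 37 − 15 = 22 and c = 0. The rule gives optimized status, 0 days and 0 changes, the minimum of both endpoints. Times for other qualifying stops run up to 7, 14 or 21 days at D = 21, 28 or 35.

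**3. Effect on the means.** The documents give no discontinuation rate and no expected values, so the following are assumptions: 100 treated; f qualifying failures; the other 100 − f complete and are optimized, with mean time m and mean number of changes k; each failure has time t and number of changes j.

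Mean time = ((100 − f)·m + f·t)/100; mean changes = ((100 − f)·k + f·j)/100.

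With m = 10 and k = 1 (days / changes):

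| f | Never changed (0, 0) | SAP-example pattern (9, 1) | Late titrator (21, 2) |
|---|---|---|---|
| 2 | 9.8 / 0.98 | 9.98 / 1.00 | 10.22 / 1.02 |
| 5 | 9.5 / 0.95 | 9.95 / 1.00 | 10.55 / 1.05 |
| 10 | 9.0 / 0.90 | 9.9 / 1.00 | 11.1 / 1.10 |
| 15 | 8.5 / 0.85 | 9.85 / 1.00 | 11.65 / 1.15 |

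With f = 10 and other completer values, in the same column order:

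- m = 5, k = 0.5: 4.5 / 0.45, 5.4 / 0.55 and 6.6 / 0.65.
- m = 15, k = 1.5: 13.5 / 1.35, 14.4 / 1.45 and 15.6 / 1.55.

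Never-changed failures lower both means whenever the completer means are above 0. For the others the direction depends on titration history.

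**4. Effect on the count.** Under the same assumptions 100 participants count as optimized, against 100 − f (98 to 85 for f = 2 to 15) if the failures are classed as not optimized. This holds for every titration pattern.

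**5. Effect on the subgroups.** PGIc and ESS are taken at early discontinuation (Protocol 8.2.2 and 8.2.3), and SAP 7.2.3 maps such data to the next visit at which they were due. The failure's data therefore exist and enter the achieved group. SAP 9.1 summarizes effectiveness in both the XYWAV Safety and XYWAV Efficacy sets. The latter is limited in SAP 6 to those who finish the study, so the misplacement concerns the XYWAV Safety version.

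**The case against.** The strongest reply is that the endpoint was never a test of benefit. Protocol 9.4.2 defines the optimized dose by its being final and unchanged, with no criterion of control or tolerability, and completers qualify under the first bullet without one. The SAP adds two duration conditions for early terminators, which makes it stricter. The figure is not shown, so what its footnote marks cannot be seen. Discontinuation reasons are reported (SAP 8.2), as are adverse events leading to withdrawal (SAP 10.2).

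Part of this stands. The footnote alone is weak support, and the stops are not hidden from the report. But the body text of SAP 5.2 carries the same meaning without the footnote. A completer was still on the drug at Visit 8, whereas a stop for an adverse event or lack of effect is recorded evidence against the dose. The disposition and adverse event tables do not correct the optimization summaries or the subgroups.

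A reader might also infer more than the text supports:

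- *That 14 unchanged days are enough.* They are not: 21 days after conversion are also required, and a stop after 14 or 20 days does not qualify.
- *That every failure gets the best score.* Only a never-changed dose gives 0 days and 0 changes; the SAP's own example has 1 change and 7 to 9 days.
- *That failures improve the endpoints in general.* Those who titrated late raise the means, and those outside the rule contribute no time value.
- *That all the SAP 9.1.7 tables are affected.* The XYWAV Efficacy version should exclude early terminators.

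**Conclusion.** The point holds in this limited form. Followed exactly, the second bullet misclassifies participants who stop for an adverse event or lack of effect, provided they meet both duration conditions. Two consequences do not depend on titration history: an inflated count of optimized participants, and misplaced ESS, PGIc and cataplexy data in the XYWAV Safety version of the SAP 9.1.7 subgroups. The flattering effect on time and number of changes is confined to failures whose dose never changed.

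The size cannot be fixed from the documents. Over the assumed range (2 to 15 such failures per 100 treated, completer mean 10 days), the mean time moves between 1.5 days down and 1.65 days up, depending on the pattern. SAP 9.1.4 lists no percentage achieved, so the count effect appears in the reported number of participants and in the subgroup sizes.

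**What to change.** In SAP 9.1.4 and 9.1.7, for analysis only:

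1. Class participants who stop XYWAV for an adverse event or lack of effect as not having achieved an optimized dose, using the discontinuation reason already summarized under SAP 8.2.
2. Report the number achieved over all participants in the XYWAV Safety set.
3. Show time to optimized dose and number of changes separately for completers and for early terminators. This is needed because removing failures who titrated late would lower the pooled mean and could itself flatter the result.

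The cost is SAP wording and programming, with no new data. SAP 8.2 lists no reason categories and Protocol 7.1 does not name lack of effect, so the recorded reasons must be mapped to the two classes before database lock. The reported number optimized may be slightly lower.

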9.1.5. Characterization of Meals Relative to Dosing

Once a participant has reached optimized dose and regimen, the investigator may decide to instruct the participant to dose without regard to food. The number of participants and percentage in each group (fasted versus without consideration of food), tabulation of the food types (regular meal, snack, drink) and percentage will be summarized.

9.1.6. Sensitivity Analyses

Not applicable

9.1.7. Subgroup Analyses

Unless specified, all endpoints will be summarized separately for participants identified as NT1 and NT2. Cataplexy attacks, ESS and PGIc will be summarized separately for those who achieved optimized dose and those that did not achieve optimized dose. Summary tables of statistics will be produced as described in Sections 9.1.1 through 9.1.3.

9.2. Exploratory Endpoints

9.2.1. Ease of Switching Medication Scale (EOSMS)

The EOSMS questionnaire will be administered in electronic format to participants at the ET or E/D visits where a participant will evaluate the process of switching from Xyrem to XYWAV with one of 5 choices (extremely easy, easy, neither easy nor difficult, difficult, extremely difficult). These answers will be tabulated with number and percent for each category of answer based on XYWAV Safety analysis set. A listing of EOSMS will be presented.

9.2.2. Forced Preference Questionnaire (FPQ)

FPQ questionnaire are given to participants at the ET or E/D visit where they will give their preference of treating their narcolepsy with Xyrem or XYWAV. The preferences will be tabulated with number and frequency based on XYWAV Safety analysis set. A listing of FPQ will be presented.

10. SAFETY AND TOLERABILITY

Unless otherwise specified, safety analyses will be based on the safety analysis set. Only summary statistics will be provided.

10.1. Exposure

10.1.1. Extent of Exposure

Exposure to Xyrem is during in baseline period and exposure to study drug XYWAV is in the Open Label Conversion and Treatment Optimization Period (intervention period) (see Section 5.2). Summary statistics, for the exposure duration (days) for Xyrem during the baseline period and XYWAV during the intervention period, number of participants, mean, standard deviation, median, and range will be tabulated.

A listing will be produced for both Xyrem and XYWAV exposure details.

10.1.2. Treatment Compliance

Compliance will be calculated for XYWAV Safety analysis set only.

XYWAV is taken as oral solution at a total salt concentration of 0.5g per mL, Table 2 shows the corresponding volume to the assigned dose level. XYWAV compliance will be calculated as the

volume of solution taken during a study period (ie, total dispensed – total returned) divided by the volume of solution that should have been taken by the participant during that intervention period, expressed as a percentage:

Compliance (%) =
$$\frac{\text{Volume of solution taken during the intervention period}}{\text{Volume of solution that should have been taken during the intervention period}} \times 100\%$$

The denominator is the sum of daily volume that should be taken according to the prescribed dose and regimen for the day.

Compliance will also be summarized by category (<75%, 75-125% and >125%) for the intervention period. A listing of compliance will also be presented.

Deviations from the prescribed treatment regimen or dosage including overdosing at greater than the maximum allowable daily dose of 9 grams or any single dose exceeding 6 grams will be summarized.

Volume of Solution (mL)
9
10
11
12
13
14
16
18

Table 2 Total Daily Volume of Solution (mL)

10.2. Adverse Events

Adverse events (AEs) occurring from the initial participant ICF signature date until the end of Safety Follow-up visit will be reported. If the Investigator becomes aware of a serious adverse event (SAE) within 30 days after the last dose of study drug XYWAV, the event must also be reported. In addition, any SAE assessed as related to study drug or procedure by the Investigator must be reported regardless of time elapsed after study termination.

Adverse events recorded in the case report form will be coded to system organ class (SOC) and preferred term using the Medical Dictionary for Regulatory Activities (MedDRA), Version 24.0. The investigator will assess the relationship of each AE to study drug. AE with a missing relationship to study drug will be reported as related in the summaries. Severity, as determined by the Investigator using National Cancer Institute (NCI) common terminology criteria for adverse events (CTCAE) version 5.0 or higher, will be classed as mild, moderate, severe, life-threatening or fatal. An AE with missing severity will be reported as missing in the summaries.

Note that participants who acquire COVID-19 or report AEs due to the COVID-19 public health emergency (eg anxiety) while on study will be coded accordingly and included in the adverse event summaries.

AEs are defined in this study as follows (Protocol Appendix 7):

- A 'Xyrem-emergent AE' refers to an AE that began or worsened in the period following signing of the informed consent and before administration of the first study intervention (XYWAV) dose (i.e., including the Screening period through the Baseline [Xyrem-stable dose and regimen] period till the first dose of XYWAV)
- A treatment-emergent adverse event (TEAE) refers to an AE that either began or worsened after administration of the first dose of study intervention drug (XYWAV) to End of Treatment (ET) period (prior to the Safety Follow-up period).
- Safety follow-up AEs are defined as occurring after the last dose date until 30 days after the last dose date
- Unless specified, the term AEs will include both Xyrem-emergent AEs, TEAEs and Safety follow-up AEs.
- Safety follow-up AEs will not be considered as either Xyrem-emergent AEs or TEAE. They will not be included into summary tables but will be presented in listings.
- Xyrem-emergent AE related summaries will be based on safety analysis set.
- TEAE related summaries will be based on XYWAV Safety analysis set.

An overall summary on Xyrem-emergent AE and TEAE with following categories will be provided:

- Subjects with any Xyrem-emergent AE/TEAE
- Subjects with any drug-related Xyrem-emergent AE/TEAE
- Subjects with any serious Xyrem-emergent AE/TEAE
- Subjects with any Xyrem-emergent AE/TEAE by severity
- Subjects with any Xyrem-emergent AE/TEAE with outcome as death
- Subjects with any Xyrem-emergent AE/TEAE leading to drug withdrawal
- Subjects with any Xyrem-emergent AE/TEAE leading to drug dose reduction
- Subjects with any Xyrem-emergent AE/TEAE leading to drug dose increase
- Subjects with any Xyrem-emergent AE/TEAE leading to drug interruption

In addition, subject incidence of Xyrem-emergent AEs/TEAEs will be summarized by following:

- SOC and PT
- PT only
- Maximum Severity by SOC and PT
- Drug-related by SOC and PT
- Xyrem-emergent AE/TEAE leading to drug withdrawal by SOC and PT

For data listings, all following will be presented:

- All AEs
- AEs with an outcome of death
- AEs leading to drug withdrawal
- Serious AEs

If a participant has multiple events with the same PT occurring in different periods, the event will be reported for each of those periods. Participant incidence of AEs by SOC and PT tables are sorted by SOCs (alphabetical order) and then by PTs (descending order) within each SOC for the overall frequency. For summaries by PT only, PTs will be sorted in descending order of overall frequency.

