9.4.4. Safety And Tolerability Analysis

All safety and tolerability analyses will be conducted in the Safety Population, based on key endpoints are summarized below. Additionally collected safety data will be summarized, as appropriate.

Adverse Event Analyses

AEs will be mapped to system organ classes (SOC) and preferred terms (PT) in alignment with Medical Dictionary for Regulatory Activities (MedDRA) criteria. AEs are defined in this study as follows ([Appendix 7](#)).

- A ‘Xyrem-emergent AE’ refers to an AE that began or worsened in the period following signing of the informed consent and before administration of the first study intervention (XYWAV) dose (ie, including the Screening period through the Baseline [Xyrem-stable dose and regimen] period)
- A treatment-emergent adverse event (TEAE) refers to an AE that either began or worsened after administration of the first dose of study intervention drug (XYWAV) to ET (prior to the Safety Follow-up period).
- Unless specified, the term AE will include both Xyrem-emergent AEs and TEAEs
- Any AEs occurring in the post-intervention Safety Follow-up period will not be considered as either Xyrem-emergent AEs or TEAE; these will not be included as part of safety and tolerability analyses, but listed separately.

Xyrem-emergent AEs (overall and during the Baseline period), TEAEs, SAEs, AEs leading to discontinuations and fatal AEs will be summarized. All AEs will be summarized by maximum severity.

The population incidence of Xyrem-emergent AEs, TEAEs, SAEs, AEs leading to discontinuations and any fatal AEs will be presented by MedRA SOC and PT categories. PT summaries may also be provided, as appropriate.

If a participant has multiple events with the same PT occurring in different periods, the event will be reported for each of those periods. Multiple increases in severity will only be counted as one AE.

Nausea Visual Analog Scale (NVAS)

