APPENDIX 4. FOOD AND DRUG DOSING DIARY**A. Drug taken: Xyrem**

Subject Number: _____

Date: _____

1. What was the time of the first dose?

(HH:MM)

2. What was the end time of the last meal prior to the first study drug dose?

(HH:MM)

3. Indicate type of meal below-

- Regular Meal- food consumed as part of dinner or planned occasion
- Snack- a bite to eat consumed between meals or prior to bed
- Beverage- a liquid drink (eg, tea, juice, milk), other than water

B. Drug taken: XYWAV

Subject Number: _____

Date: _____

1. What was the time of the first dose?

(HH:MM)

2. What was the end time of the last meal prior to the first study drug dose?

(HH:MM)

3. Indicate type of meal below-

- Regular Meal- food consumed as part of dinner or planned occasion
- Snack- a bite to eat consumed between meals or prior to bed
- Beverage- a liquid drink (eg, tea, juice, milk), other than water

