7.2.3. Visit Windows

Except where specified, all data will be summarized using the CRF visit at which the data was collected. Where data is captured at an Early Termination visit, those data will be summarized with the regular visit at which the assessment would have been captured, relative to the study period during which the participant withdrew. For example:

- If a participant early discontinues during the Baseline Period, i.e. prior to the first dose of XYWAV, then data should be mapped to Visit 3.
- If a participant early discontinues during the Intervention Period, i.e. after at least one dose of XYWAV, then data should be mapped to the next scheduled visit at which those data would have been captured, based on the Schedule of Assessments.

For data captured independent of a CRF visit, eg, Adverse Events, Concomitant Medications and Cataplexy Diary, the following rules will apply:

- If the reported date is on or prior to first dose of XYWAV then the data will be considered to be included into the Xyrem Baseline Period for summaries
- If the reported date is after the first dose of XYWAV while on or prior to the completion of treatment or early discontinuation, then the data will be considered to be included into the XYWAV Intervention Period for summaries.

Unscheduled visits in general will not be mapped (excluded from analyses) when the corresponding scheduled visit is present. Unscheduled visits will only be mapped when the scheduled visit is missing. If more than 1 unscheduled assessments are available, choose the one with the assessment date closer to the target study day specified below, if 2 assessments are equally close to the target day (but on different sides), the latter assessment will be chosen. In addition, unscheduled visits with the assessment date earlier than the date of first dose of XYWAV, or participants early discontinue the study prior to the first dose of XYWAV, the data can only be mapped up to Visit 3. If the assessment date is later than the date of first dose of XYWAV, the unscheduled data should not be mapped to any visit prior to Visit 3.

Study Period	Study Visit	Target Study Day
Baseline	Visit 2	1
Intervention	Visit 3	15

Intervention	Visit 4	22
Intervention	Visit 5	29
Intervention	Visit 6	36
Intervention	Visit 7	43
Intervention	Visit 8	57

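### SAP 10.2 gives two conflicting ends to the XYWAV adverse-event window, and its exclusion rule removes events between the last dose date and the ET or E/D visit from the TEAE and withdrawal tables

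*SAP*

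**What the plan says.** Three places run the XYWAV window to the end of treatment or discontinuation:

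- Protocol 9.4.4 defines a TEAE as an event that "began or worsened after administration of the first dose of study intervention drug (XYWAV) to ET (prior to the Safety Follow-up period"). It excludes only events in the Safety Follow-up period, which under Protocol 4.1 follows ET or E/D.
- The TEAE bullet in SAP 10.2 also runs "to End of Treatment (ET) period (prior to the Safety Follow-up period").
- SAP 7.2.3, which names adverse events among the data it covers, states that for dates after the first XYWAV dose and "on or prior to the completion of treatment or early discontinuation, then the data will be considered to be included into the XYWAV Intervention Period".

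The next bullet of SAP 10.2 uses a different boundary: "Safety follow-up AEs are defined as occurring after the last dose date until 30 days after the last dose date". A later bullet gives the consequence: "Safety follow-up AEs will not be considered as either Xyrem-emergent AEs or TEAE", and then "They will not be included into summary tables but will be presented in listings".

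The AE summaries in SAP 10.2, including the table of events leading to drug withdrawal by SOC and PT, count Xyrem-emergent AEs and TEAEs only. SAP 7.6, which lists changes from the protocol, mentions added analysis sets and CTCAE grading but no last-dose cut-off.

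**The concern.** The two SAP 10.2 definitions overlap. An event dated after the last dose but no later than the ET or E/D visit is both a TEAE and a safety follow-up AE. The only sentence that settles the overlap is the exclusion bullet, and it removes the event from the tables. A programmer who follows the section literally would do the same.

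Night dosing brings the overlap close to the drug effect. Protocol 5.3.4 has the drug taken in bed, and the SAP rule works on dates. If the final dose is taken before midnight, a reaction after midnight or the next morning carries the following date. If that reaction is why the participant stops, the earlier date remains the last dose date.

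AEs are the first key endpoint in this switch study, and tolerability relative to Xyrem is one of its questions (Protocol 2.1). Any event lost this way makes the XYWAV tables look more favourable. With about 100 participants, one or two reclassified withdrawals would be visible.

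**Working it through.** The documents give no figure to reproduce, so the check is a count of days and dates under the competing rules.

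**1. Days that meet both definitions.** SAP 7.2.3 supplies an example with the first XYWAV dose on the night of Day 15 and early termination on Day 20. It also gives a Visit 8 target of Day 57. The last-dose night is my assumption. Overlap days are those after the last dose date, up to and including the ET or E/D visit.

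| Case | Last dose (assumed) | TEAE days | Overlap days | Share |
|---|---|---|---|---|
| E/D Day 20 | night of Day 19 | 15–20 (6) | Day 20 (1) | 1/6 = 16.7% |
| E/D Day 20 | night of Day 16 | 15–20 (6) | Days 17–20 (4) | 4/6 = 66.7% |
| E/D Day 20, single dose | night of Day 15 | 15–20 (6) | Days 16–20 (5) | 5/6 = 83.3% |
| Completer, Visit 8 on Day 57 | night of Day 56 | 15–57 (43) | Day 57 (1) | 1/43 = 2.3% |

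Taken over the 6-week period (42 days), the completer share is 1/42 = 2.4%. In its own example SAP 7.2.3 counts Days 16–20 as the last XYWAV week, so it treats the discontinuation day as a XYWAV day. Under the exclusion bullet of SAP 10.2, an AE on that same day would be follow-up if the last dose was the night before.

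**2. The midnight effect.** Take a last dose at clock time t before midnight and an assumed 8-hour span after it. The share of the span that falls on the next date is (8 − (24 − t))/8.

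- 21:00: (8 − 3)/8 = 62.5%
- 22:00: (8 − 2)/8 = 75%
- 23:00: (8 − 1)/8 = 87.5%
- 23:30: (8 − 0.5)/8 = 93.75%, about 94%
- 00:30, dated after midnight: 0%

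These are shares of time, not of events.

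**3. Effect on the withdrawal table.** Let W be AE withdrawals per 100 participants and f the share whose causal event starts after the last dose date. The table then shows W × (1 − f). Neither W nor f is in the documents. With W = 5 assumed:

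- f = 0: 5
- f = 0.25: 3.75
- f = 0.5: 2.5
- f = 1: 0

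**4. Worsening.** Protocol Appendix 7 records an increase in severity as a new AE and closes the old one. A worsening after the last dose date therefore has its own later onset and falls under the same exclusion. The milder event, if it began earlier on XYWAV, stays in the tables.

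**The case against.** A reader might infer that the SAP has settled on the last dose date and that XYWAV withdrawals will be systematically understated. The documents do not support either reading.

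- **The cut-off is one side of a contradiction.** The SAP 10.2 TEAE bullet, SAP 7.2.3 and Protocol 9.4.4 all run to ET or discontinuation. The exclusion bullet favours the last-dose reading without making it the only one.
- **The direction is known but the frequency is not.** Nothing shows that AEs ending treatment mostly begin after the final dose. An event that starts on an earlier XYWAV night, persists and leads to stopping remains a TEAE.
- **The dating convention is not stated.** The diary asks "What was the time of the first dose" and does not time later doses that night. But the diary is not named as the source of the last dose date, because Protocol 6.4 puts intervention start and stop dates in the eCRF. Doses may be taken up to three times a night. If the last one falls, and is dated, after midnight, a reaction later that night shares its date.
- **The events are not lost altogether.** SAP 10.2 lists all AEs, AEs leading to withdrawal, serious AEs and deaths. SAP 8.2 tabulates discontinuations with reasons by period. Nausea also has its own scale, collected before E/D where possible.

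All of this stands and limits the claim. It does not remove the conflict: listings give no incidence, and disposition reasons are not summarised by SOC and PT.

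**Conclusion.** The point holds as an internal contradiction that needs to be reconciled. As written, SAP 10.2 takes any AE that starts or worsens after the last dose date, but on or before the ET or E/D visit, out of the TEAE and drug-withdrawal tables. It does so against Protocol 9.4.4 and SAP 7.2.3, and SAP 7.6 does not declare it.

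For completers the size is small, about 1 day in 42 to 43, assuming the last dose is the night before Visit 8. For early discontinuers it depends on the gap between last dose and E/D and on how doses and AEs are dated. The loss may range from none to all of the AEs that begin after the final dose, and the documents give no rate to narrow that range. The study is descriptive, so no test is affected. What is at risk is the accuracy of the reported XYWAV incidences.

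**What to change.** In SAP 10.2, define a TEAE as onset or worsening after the first XYWAV dose up to and including the ET or E/D visit, as in Protocol 9.4.4 and SAP 7.2.3. If no ET or E/D visit takes place, run the window to the calendar day after the last XYWAV dose. Start safety follow-up AEs after that point, so that the two categories cannot overlap. If the sponsor prefers a last-dose rule, it should be justified, cover the night and day after the final dose, and appear in SAP 7.6.

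The fix should not count every AE that led to withdrawal as a TEAE regardless of its date. That would have no end point and could bring in Safety Follow-up events that Protocol 9.4.4 excludes.

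The cost is a change of wording and one derivation, with no new data. A few events between the last dose and a late E/D visit will count as TEAEs, which makes the XYWAV figures slightly less favourable.
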